After receiving interest of a potential participant and consent form has been received researchers would then reach out via phone call to provide a more comprehensive description of the project, screening, and informed consent. Participants will be fully informed that they are free to stop their participation at any time. Candidates will need to pass a brief quiz testing their understanding that participation is completely voluntary. Participants will be required to answer questions demonstrating that they understand what type of data will and will not be collected from them over the upcoming months (self-report and FOCUS use data). Each question will need to be answered correctly before individuals can proceed to provide consent. Individuals who commence the study will be assigned to their sites practice facilitator (external or internal). Randomization will occur at the site level with equal representation of urban and rural settings in each implementation arm.

Staff Participants who will participate in on-site data collection evaluating implementation outcomes and clinic characteristics will be purposively selected from CMHC (both study arms) and from CMHC

administration/budget/finance offices (for costing). The assessment evaluating implementation outcomes will be fully explained to staff participants via webpage (hosted by Qualtrics), where staff can check a box to indicate they are willing to participate. Assessments time points will be at 0M (prior to their patient beginning treatment), then at roughly 3M (time-point after the patient completes treatment). The confidential survey takes 20-30 minutes to complete (questions are included in the supportive documents) and staff will be compensated \$20 in the form of an Amazon gift card for their time. Staff key informants will complete interviews with a trained member of the research team related to costing, including questions about services and effort put towards the study. Key informant interviews will last approximately 60 minutes and be audio-recorded, and later transcribed. Numbers will be provided at aggregate levels, or if treatments were specified, would not identify the individual.

4.2 Recruitment materials.

a. What materials (if any) will you use to recruit and screen subjects?

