5 PROCEDURES

study.

5.1 Study procedures. Using lay language, provide a complete description of the study procedures, including the sequence, intervention or manipulation (if any), time required, and setting/location. If it is available and you think it would be helpful to the IRB: Upload a study flow sheet or table to the **Supporting Documents** SmartForm in **Zipline**.

For studies comparing standards of care: It is important to accurately identify the research procedures. See UW IRB POLICY: Risks of Harm from Standard Care and the draft guidance from the federal Office of Human Research Protections, "Guidance on Disclosing Reasonably Foreseeable Risks in Research Evaluating Standards of Care"; October 20, 2014.

About the study:

This study is a multi-site site hybrid type III effectiveness/implementation study. The intention of this study is to examine the delivery of FOCUS within two treatment models. One, where the app is delivered through an internal facilitator embedded within a mental health clinic (study site), the other, involves an external facilitator delivering the intervention (staff at UW). Both facilitators help participants install, use, and incorporate the app's strategies into their own coping skillset.

The project will involve recruiting outpatients with schizophrenia spectrum disorder who receive mental health services at CMHCs in WA for participation in a randomized controlled trial (15 at each CMHC; n=300). Patient participants will engage in a 3-month long mHealth intervention called FOCUS which involves use of a smartphone system in their own environment and weekly phones calls with a practice facilitator that is based at the UW (EF model) or the CMHC where they receive care (IF model). Participants enrolled in the IF arm may also have in-person meetings with their agency-facilitator at their CMHC or in the community.

Arm I: All the same research procedures as ARM II, FOCUS delivery to participants is through an Internal Facilitator (staff member of study site who is identified and trained to serve as a navigator to the FOCUS app (technology, program use and application of strategies to their treatment plan)).

Arm II: All the same research procedures as ARM I, FOCUS delivery to participants is through an External Facilitator (UW staff who will be trained to serve as a navigator to the FOCUS app (technology, program use and application of strategies to their treatment plan)).

Description of the mHealth intervention:

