Randomization will occur at the level of the clinic and will be balanced within study arm by number of patients served and rural/urban designation. Study sites (k=20) will vary in staffing and services capacity. Sites will either be randomized to have an internal facilitator (IF) or external facilitator (EF). The internal and external facilitators will work to engage participating organizations, practitioners, and patients throughout the study which includes sending email and placing phone calls with participating organizations, practitioners and patients in order to conduct the study (i.e., schedule appointments, request materials, etc.). They will provide updates about study progress and will maintain and request data from the study sites.

Patient Participants

After consenting into the study, patient participants will receive a phone call prior to each assessment (OM, 3M, 6M) letting them know they will receive a text or email (for those who have identified trouble receiving text messages) with the assessment URL and to provide instructions for how to complete the assessment (ensure they are in a private place, have reliable data for transmission, will take aprox. 20-30 minutes to complete, etc). Participants will then receive the web-based baseline assessment via text and will be asked to complete it in a private and quiet space. For those who have expressed difficulty completing the assessment through the web-based assessment, a phone call can be conducted with trained assessor to ask questions directly over the phone. Afterward, they will be asked to meet with their assigned facilitator (IF/EF) to install the FOCUS app on their phone, describe how to use it and set up a time for their weekly calls. This may be done via phone call, or video call, whichever is preferred by the participant. Participants will continue to use the program for 3 months in their own environments, along with participating in weekly calls to discuss what they've learned in the FOCUS app and how those strategies can help support their symptom coping strategies.

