## UNIVERSITY of WASHINGTON

Analytic Approach. Our analyses seek to test the overall effect of our implementation strategies on implementation outcomes (Aim 1), mediators and moderators of those effects (Aim 2), and the impact of the strategies on patient outcomes (Aim 3). In Aim 1, the dependent variables of interest will be penetration and provider acceptability assessed at baseline (prior to initiation of the facilitation strategies), at 3 months (following the completion of the facilitation period), and at 6 months (following 3 months of having no exposure to facilitation). Given the nested data (i.e., time nested within clinicians and clinicians nested within agencies), analyses will rely on 3-level mixed effects regression models. Negative binomial regression with log offsets will be used to model rates, and linear regression will be used to model continuous outcomes. For all models, our independent variables of interest will be a binary indicator of internal versus external facilitation (measured at the organizational level), time, and their interaction. The magnitude and statistical significance of the interaction term will estimate the effect of the implementation strategy on change, or "growth," in outcomes over time. The impact of the intervention strategy on each outcome at each time will also be derived from these models. In addition, we will aggregate facilitylevel data and estimate the average weighted cost metrics across the sample of sites. Future commercial pricing of mHealth technology is unknown, so we will run scenarios that have different ranges of costs for FOCUS and explore the impact on the total program costs.

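### The main linear models for 20 clinics randomised with balance should name the balancing factors, an agency-level random effect for time, and a t reference on site-level degrees of freedom

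*SAP*

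**What the plan says.** **Design.** Protocol section 5.1 (Study Sites) randomises clinics and says that allocation "will be balanced within study arm by number of patients served and rural/urban designation". Section 4.1 adds: "Randomization will occur at the site level with equal representation of urban and rural settings in each implementation arm". Section 5.1 also says: "Study sites (k=20) will vary in staffing and services capacity". In the internal arm the facilitator is a "staff member of study site who is identified and trained to serve as a navigator to the FOCUS app".

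**Analysis.** For Aim 1 (SAP, Analytic Approach), "analyses will rely on 3-level mixed effects regression models", with time within clinicians within agencies. The "independent variables of interest will be a binary indicator of internal versus external facilitation (measured at the organizational level), time, and their interaction". The target is stated as follows: "The magnitude and statistical significance of the interaction term will estimate the effect of the implementation strategy on change". The strategy effect at each visit is to come from the same models. Continuous outcomes get linear models. For rates: "Negative binomial regression with log offsets will be used to model rates". Aim 3 applies the same techniques with patients in place of clinicians.

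**What is not stated.**
- The random terms at agency level. The Aim 2 mediation text mentions a growth parameter that varies between clinicians; nothing similar is given for agencies.
- The reference distribution, the choice of ML or REML, and any small-sample correction. The SAP names only MPlus and likelihood-based handling of dropout.
- Adjustment for the balancing factors in the main models. Rural/urban enters only as a moderator. Number of patients served appears nowhere in the SAP.

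**The concern.** The randomised unit is the clinic, so a test of strategy should draw its error from variation between 20 sites, after removing what the allocation was balanced on. The three gaps bear on this in different ways.

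- **Balancing factors.** Balance removes their contribution from the arm difference, but an unadjusted model leaves it in the error term. The standard error is then too large and precision is lost.
- **Reference distribution.** With 20 sites, a normal reference is too narrow, more so under ML.
- **Agency random effect for time.** Strategy by time is the main test. Sites may well change at different rates, since staffing varies and internal facilitators are local staff. If an analyst fitted only an agency intercept, patients or clinicians would count as independent units of change.

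Two analysts could follow the text and report different intervals. The Aim 2 models are built on the same base.

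**Working it through.** **Inputs from the SAP (Power Analysis).** 20 sites; 15 patients and 5 clinicians per site; between-organization ICC 0.19; between-patient ICC 0.45; between-provider ICC 0.30; alpha 0.05 two-sided. Total variance is set to 1 and allocation is assumed 10:10. No document gives a variance for site differences in change, or the share of site variance that the balancing factors explain. Both are assumed below over a range.

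**The plan's own figure.** The SAP states a detectable d of 0.44 for patient outcomes. A single-visit reading gives (1.960 + 0.842) × √(0.2 × (0.19 + 0.81/15)) = 2.802 × √0.0488 = 0.62, not 0.44. The SAP gives no formula and does not say which contrast was powered, so this does not show 0.44 to be wrong. Nothing below uses it.

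**1. Balancing factors, arm difference at one visit.** The variance of a site mean is V = 0.19 + 0.81/15 = 0.244. If the factors explain a share R² of site variance, f = 0.19 R². With the factors balanced across arms, the true error variance is V − f. The unadjusted residual variance has expectation (V − f) + (20/18) f. So the SE ratio is √(1 + (20/18) f/(V − f)).

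| R² (assumed) | f | SE ratio |
|---|---|---|
| 10% | 0.0190 | 1.046 |
| 25% | 0.0475 | 1.126 |
| 40% | 0.0760 | 1.226 |

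The unadjusted test is then conservative. In a simulation check its error with t on 18 df was 2.9% at R² = 25% and 1.8% at 40%, against about 5% with adjustment and t on 16 df.

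In a balanced linear model, constant main effects of the factors do not change the strategy-by-time test, so their time interactions are needed for any gain there. With V = w + 0.55/15, where w is the site-by-visit variance, the same formula gives ratios of 1.019/1.051/1.084 at w = 0.019 and 1.033/1.087/1.151 at w = 0.0475.

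**2. Normal reference, arm difference at one visit, factors not prognostic.**
- REML, 18 df: 2P(t18 > 1.96) = 6.6%.
- ML, 18 df: 2P(t18 > 1.96 √(18/20)) = 7.9%.
- ML with the two factors added, 16 df: 2P(t16 > 1.96 √(16/20)) = 9.9%.

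Adding the factors while keeping ML and z therefore makes the error worse. Adjustment and the t reference belong together.

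**3. Strategy by time if no site slope is fitted.** Let e be the residual variance and m the number per site. The true variance of the contrast exceeds the model's by the ratio (w + e/m)/((w + e)/m), and the type I error is 2P(Z > 1.96/√ratio). Assume w is 5%/10%/25% of 0.19, that is 0.0095/0.019/0.0475.

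| Case | Ratio | Type I error |
|---|---|---|
| Patients, m = 15, e = 0.55 | 1.238/1.467/2.113 | 7.8%/10.6%/17.8% |
| Clinicians, m = 5, e = 0.70 | 1.054/1.106/1.254 | 5.6%/6.2%/8.0% |

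First patient entry: (0.0095 + 0.0367)/(0.5595/15) = 0.0462/0.0373 = 1.238. If 0.19 and 0.45 are meant to add, e = 0.36 and the patient error is 9%/13%/23%.

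**4. Strategy by time if a site slope is fitted.** Simulation of 12,000 null trials per case, 15 patients per site, four assumed strata of 6, 4, 4 and 6 sites, factors included, w as in step 3.

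| Method | Type I error |
|---|---|
| REML with slope, z | 5.4%/5.8%/6.8% |
| REML with slope, t16 | 3.7%/4.2%/5.0% |
| Regression of 20 site mean changes, t16 | 4.9%/4.8%/5.0% |

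With assumed site sizes of 5 to 25, the site-means regression gave 5.0%/5.1%/4.9%.

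**The case against.** The strongest reply is that the SAP contains no error. A 3-level model leaves room for an agency slope, the SAP describes its test as one of growth, and strategy is placed at organizational level. Naming variables of interest does not close the list of covariates. If a slope is fitted, step 4 shows that z costs little. All of this stands.

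Several stronger readings are tempting, and the documents do not support them.
- **The trial will test at 8% to 18% error.** This needs both a no-slope reading that the SAP does not state and a site-by-visit variance that no document gives.
- **The largest rates apply to the implementation outcomes.** They belong to patient outcomes in Aim 3. For continuous clinician outcomes in Aim 1 they are 6% to 8%.
- **Leaving out the balancing factors invalidates the test.** It makes the test conservative. The loss is precision, and rural/urban is already modelled as a moderator.
- **The rate outcomes have a known inflation.** The SAP's negative binomial mixed model was not fitted here, so no error rate is claimed for it.
- **Fitting a slope gives up power that the plan claims.** The SAP states no power for a no-slope interaction test, so there is no such baseline to lose.
- **The balancing rule is a defect because its details are not given.** That is missing detail, not a flaw in the design.

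**Conclusion.** The point holds as a modest improvement to the specification. Twenty clinics are randomised with balance on two factors, and the main Aim 1 and Aim 3 models name neither factor, nor an agency random effect for time, nor a small-sample reference. The firmest figures are those for a normal reference at one visit when the factors are not prognostic, which need no assumed variance: 6.6% under REML, 7.9% under ML and about 10% under ML with the factors added. The precision loss depends on an assumed share of site variance. The strategy-by-time inflation is conditional on both assumptions in step 3. All figures are for continuous outcomes without dropout; the closed forms also take equal site sizes.

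**What to change.** In the SAP's main linear models for Aims 1 and 3:

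1. Include rural/urban and site size, each with its interaction with time.
2. Give the agency level a random slope for time, or a site-by-visit effect if time is categorical.
3. Test strategy effects with t on about 16 site-level df. If MPlus cannot provide this, confirm with a regression of the 20 site mean changes on strategy and the two factors, using t16. The two agree exactly only with balanced data.

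A permutation test over the permitted allocations is optional.

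**Cost.** The change is to SAP wording; no data or sites are added. It uses two site-level df plus two time-interaction terms (four if time is categorical). Replacing z by t16 widens intervals by 2.120/1.960 − 1 = 8%, and 80% power becomes about 75% at the same SE, before any gain from the factors. When the site slope variance is near zero, REML with t16 is slightly conservative: 3.7% to 4.0% at w = 0.0095. If sites do differ in change as assumed, patient-outcome intervals for strategy by time are 11%/21%/45% wider than without a slope, which corrects a standard error that was too small.

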2 PARTICIPANTS

2.1 Participants. Describe the characteristics of the subject populations or groups, including age range, gender, health status, and any other relevant characteristics.

Patient participants will all be over the age of 18, include all genders, use English, own a smartphone with data plan has a diagnosis of schizophrenia-spectrum disorders and receive services from a participating clinic.

2.2Inclusion and exclusion criteria. Describe the criteria you will use to decide who will be included in your study from among interested or potential subjects. Define any technical terms in lay language.

Patient inclusion criteria: a) Chart diagnosis of SSD (i.e., schizophrenia, schizoaffective disorder, schizotypal disorder, delusional disorder, or schizophreniform disorder; b) 18 years or older; c) English-speaking; d) Own a smartphone that can support FOCUS and active data plan.

[figure not shown]
Patient exclusion criteria: 1) Used FOCUS in the past; 2) Plan to move or discontinue CMHC services in the upcoming 6 months.

CMHC staff will be asked to complete an online survey evaluating implementation outcomes and clinic characteristics. Staff from CMHC administration/budget/finance offices will also help inform costing through the use of de-identified data.

Staff inclusion criteria: a) Staff members at a participating study site; b) 18 years or older.

- **(2.3) Prisoners**. IRB approval is required in order to include prisoners in research, even when prisoners are not an intended target population.
 - a. Do you intend to deliberately recruit prisoners or obtain prisoner data/specimens?

See the WORKSHEET: Prisoners for the definition of "prisoner".

	b. Is your research likely to have subjects who become prisoners while participating in your study?		
	For example, a longitudinal study of youth with prisoners at some point during the study.	drug problems is likely to have subjects who will be	
	No Yes → If yes, if a subject becomes a prisoner while participating in your study, will you continue the study procedures and/or data collection while the subject is a prisoner? No Yes → If yes, describe the procedures and/or data collection you will continue with prisoner subjects		

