The FOCUS application uninstalls at 3 months and then the 3 month web-based outcome assessment will be sent via text and will ask participants to complete it in a private and quiet space. Once again those who express difficulty completing the assessment through the web-based platform can request a call with an assessor on the research team. Participants who complete treatment will be mailed out a certificate of completion to their home address or clinic (based on participant's choice). They will no longer have access to the app, nor will participate in weekly calls for the next 3 months. They would then be sent another assessment at 6 months to complete.

Patient Participant Assessment:

Patient participants will receive a text from researchers just before their assessment date providing instructions on how to complete the online assessment. They will then be invited to conduct assessments at 0, 3, and 6 months via embedded link to a secure study portal (Qualtrics). For participants who need additional assistance, they can come into the participating clinic to complete on a tablet provided by the research team. Patient participants will receive \$30 compensation for each completed assessment (estimated completion time < 45 minutes) for a maximum of \$90 compensation (Plus additional \$10 each assessment to compensate data transmission or travel to site if more assistance is necessary). All participants will be paid for each assessment, but they will not be compensated for engagement in the intervention; assessments are administered to everyone enrolled in the study regardless of how/whether they engaged in FOCUS (note: all patient participants own working smartphones as part of inclusion criteria).

Assessments include questions about psychiatric treatment and hospitalizations, along with other measures of mental health including depression, anxiety, hearing voices, and recovery:

- Demographics and other characteristics
- PhQ9
- GAD-7
- Hospitalization- days hospitalized, no identifiers will be captured.
- ISI: Insomnia Severity Index
- Green Paranoid Thoughts Scale
- Symptom Checklist SCL-9Hamilton Program for Schizophrenia Voices Questionnaire (HPSVQ)
- Recovery Assessment Scale (RAS)
- Illness Management Recovery Scale (IMRS)
- Working Alliance Inventory (3M only)
- mHealth Mastery Measure (3M only)
- AIM
- Satisfaction

Information we plan to collect from EMR data:

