- A list of active participants will be generated either through culling EMR data or talking with clinical teams that will serve as the primary list for their clinical teams to approach to describe the study and gauge interest.
- Services billed- no identifiers will be shared with the research team

Mental Health Provider Participants:

Select mental health providers will be invited to complete an online assessment with the research team. Staff participants will be invited to complete a confidential online survey. This includes exposure to the FOCUS app, if strategies or the program was incorporated into their treatment plans, and perceptions of how the program was adopted and implemented at their clinic.

Mental Health Provider Assessment:

Providers who receive FOCUS data

- Offered mHealth, i.e., the percent of each practitioner's eligible patients who are offered FOCUS
- Treatment Initiation, i.e., percent of consenting patients who followed their practitioner's guidance and went on to download FOCUS onto their smartphone and interact with the system at least once. Dashboard Use, i.e., the average number of times each practitioner logs on to the online FOCUS dashboard to view their individual patients' uploaded FOCUS data

The following will be captured via online confidential** survey (Qualtrics):

- The perception among practitioners that an innovation is agreeable, palatable, or satisfactory. (Measured via AIM / IAM / FIM).
- ORIC: Organizational Readiness for Implementing Change

Providers at the clinic who may not have been directly involved with the FOCUS Intervention (to provide contextual factors) through online confidential survey (Qualtrics):

- Organizational Readiness to Change Assessment (ORCA)
 - CMHC staff participants will complete 23 items using a 5-point bipolar rating scale (1-Strongly agree to 5-Strongly disagree). Constructs evaluated include clinical cooperation within the practice, clarity in patient care goals and process, level of support (e.g., training, budget, staffing) and typical receptivity to guidance (staff) and feedback (leadership).
- Absorptive capacity will be measured among CMHC practitioners who were engaged in IF or EF implementation at 0, 3, and 6 months using the 14-item ACAP Scale.
 - o The ACAP Scale evaluates dimensions of absorptive capacity including
 - Acquiring (e.g., searching for new information, motivation to use information)

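### Dashboard log-ins and treatment initiation carry no information before facilitation starts; if modelled as log-link rates, strategy × time does not estimate the IF–EF effect on them, and the SAP does not name the month-3 contrast as the test

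*SAP*

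**What the plan says.** The SAP's Analytic Approach (Aim 1) has two outcomes, provider acceptability and penetration, with this timing: "assessed at baseline (prior to initiation of the facilitation strategies), at 3 months (following the completion of the facilitation period), and at 6 months". For the model: "Negative binomial regression with log offsets will be used to model rates"; continuous outcomes get linear regression. Every model contains strategy, time and their interaction. On the readout: "The magnitude and statistical significance of the interaction term will estimate the effect of the implementation strategy on change". It then adds: "The impact of the intervention strategy on each outcome at each time will also be derived from these models". It does not state how time is coded, which measures count as rates, or which of the two readouts decides. In Aim 2, path b of the mediation model is defined on the clinician-level growth parameter.

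Protocol section 5.1 lists three provider-uptake measures: the percent of eligible patients offered FOCUS; treatment initiation, a percent of consenting patients who download and use the app; and dashboard use, "the average number of times each practitioner logs on to the online FOCUS dashboard" to look at data their patients have uploaded. Neither document says that these three make up penetration. They are the only provider-uptake measures listed, so that is the natural inference.

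Three further protocol statements fix what can happen when:
- Section 2.2: "Patient exclusion criteria: 1) Used FOCUS in the past".
- Section 5.1, following consent and the baseline assessment: "Afterward, they will be asked to meet with their assigned facilitator (IF/EF) to install the FOCUS app on their phone".
- Section 5.1: "The FOCUS application uninstalls at 3 months".

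**The concern.** Before facilitation no enrolled patient has the app and none has used it before. There are no uploaded data to view, so log-ins are zero in both arms by construction. Treatment initiation is 0/n, or 0/0 if nobody has consented yet. The month-0 value of these two measures therefore says nothing about either arm.

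A strategy × time term asks how the IF–EF difference changes from that starting point. On a log scale the starting difference is the log of 0/0. The quantity to which the SAP attaches statistical significance may then be undefined, or may be close to zero when one strategy truly produces twice the use. Two results from one model could disagree, with no rule for which counts. Penetration is a main outcome of a trial whose purpose is to compare implementation strategies, and the growth parameter is carried into the Aim 2 mediation.

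**Working it through.** **1. Inputs.** From the documents: assessments at 0, 3 and 6 months; 20 centres × 5 clinicians = 100 providers; two-sided alpha 0.05; log-link negative binomial (NB) for rates. Assumed, because the documents give no figures: mean log-ins at month 3 of 6 (EF) and 12 (IF), several levels of month-6 use, and the variances in step 6.

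**2. The plan's own provider-level figure, d = 0.55.** No formula is given. An unclustered comparison of 50 v 50 at one time gives (1.960 + 0.842) × √(2/50) = 0.560, or 78.5% power at 0.55. A mean of three occasions, borrowing the patient-level site ICC of 0.19, gives 0.560 × √[(1 + 4 × 0.19) × (1 + 2 × 0.30)/3] = 0.543. A baseline-to-follow-up change gives 0.560 × √[2(1 − 0.30)] = 0.663. The figure does not show which contrast is meant, and nothing below depends on it.

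**3. Log link, categorical time.** Interaction at month 3 = log RR(month 3) − log RR(month 0), and RR(month 0) = 0/0. Fitting expected counts 0/6/0 (EF) and 0/12/0 (IF), the intercept after 10, 25 and 50 iterations is −9.6, −24.6 and −38.8. The interaction's standard error (SE) is about 1×10², 2×10⁵ and 2×10⁷. The month-3 contrast stays at log 2 = 0.693. The routine also prints 0.693 for the interaction, but only because both baselines diverge together; it carries no information.

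**4. Log link, linear time.** In a Poisson fit the slope b of each arm depends only on the count-weighted mean time m: with r = exp(3b), (3r + 6r²)/(1 + r + r²) = m.
- 0/6/3 and 0/12/6 both have m = 4. The slopes are equal, the interaction is 0, and the doubling goes into the arm main effect (0.693).
- 0/6/3 has m = 36/9 = 4, so r = 1.686 and b = 0.1741. 0/12/3 has m = 54/15 = 3.6, so r = 1.356 and b = 0.1015. The interaction is −0.0726 per month although IF doubles log-ins at month 3.

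The same expected counts, with NB dispersion 0.5:

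| EF v IF (months 0/3/6) | Poisson interaction per month | NB interaction per month |
|---|---|---|
| 0/6/0 v 0/12/0 | 0 | 0 |
| 0/6/3 v 0/12/6 | 0 | 0.057 |
| 0/6/6 v 0/12/12 | 0 | 0.061 |
| 0/6/3 v 0/12/3 | −0.073 | −0.051 |

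**5. Linear regression.** With linear time the slope weights over 0/3/6 are proportional to (−1, 0, 1), so the slope is (y₆ − y₀)/6. Month 3 drops out, and with y₀ = 0 the interaction is the month-6 difference alone, after the app has gone. With categorical time the interaction is (12 − 0) − (6 − 0) = 6, exactly the month-3 difference.

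**6. Illustrative simulation.** Three-level NB model, 20 × 5 clinicians, EF mean 6, log-scale SD 0.4 (site) and 0.5 (clinician), NB size 2, month 0 = 0; 200 trials per row (150 for the tripling). Percent rejecting:

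| True IF/EF ratio; month-6 use as % of month 3 | Interaction, model-based SE | Interaction, site-robust SE | Month-3 contrast, linear time | Month 3 only |
|---|---|---|---|---|
| 2; 50% | 0 | 54 | 76 | 75 |
| 2; 100% | 1.5 | 46.5 | 76.5 | 75 |
| 2; nil | 0 | not reported | 55.5 | 75 |
| 3; 50% | 0 | 93 | 98 | 97 |
| 1 (null); 50% | 0 | 7.5 | 7.5 | 7.5 |

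The robust rejections come from misfit. In the first row the true ratio after start is constant at 2, yet the fitted ratio runs from 1.51 at month 0 to 2.44 at month 6. A simpler NB model (site SD 0.3, site-robust SE, 18 df, 500 trials) rejects on the interaction in 29% and 32% for the first two patterns and 0% for nil month-6 use, against 75–78% for the month-3 contrast. For 0/6/3 v 0/12/3 it rejects in 31% with a negative mean coefficient, against 79% at month 3.

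**7. Treatment initiation.** If nobody has consented at month 0, 100 of the 20 × 5 × 3 = 300 clinician-by-time rows have offset log(0).

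**The case against.** The strongest reply is that the usable test is already planned. The SAP derives the strategy effect at each time, and under categorical time its month-3 contrast is the test recommended here: keeping or dropping the all-zero month-0 row moves the estimate and SE by at most 1.4×10⁻⁸. Under linear time it still has about 76% power in the simulation when use continues. That stands, and it makes the remedy small. It does not remove the problem, because the SAP ties size and significance to the interaction, does not rank the two readouts, and does not state the time coding.

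Second, change and level are different estimands, and the SAP's power section takes an exploratory stance without multiplicity adjustment. Reporting both is legitimate. But under the log link the change estimand has no defined starting value for these two measures.

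Third, a reader might infer that strategy × time is invalid for penetration as a whole. The documents do not support that. Dashboard use is described as an average number of log-ins, so linear regression cannot be excluded, and with categorical time the interaction is then the month-3 difference. Percent offered can precede baseline and is unaffected, as is acceptability.

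Fourth, a reader might infer that the Aim 2 mediation fails. That is not established. In a simulated mediator effect on log-ins, the mediator × time term was detected in 0%, 71–72% or 97–99% of trials, depending on the SE and on whether a mediator main effect was included. That model had random intercepts only, whereas the SAP's wording suggests clinician-specific growth.

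**Conclusion.** The point holds in a bounded form and should be fixed. If dashboard log-ins and treatment initiation are analysed as log-link rates, strategy × time does not estimate the IF–EF effect. With categorical time it is not estimable. With linear time a constant ratio after start goes mainly into the arm main effect, so the interaction can be zero, small or of the wrong sign while month 3 shows a doubling. With linear regression and linear time it reflects only month 6 minus month 0. With linear regression and categorical time there is no problem.

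The non-estimability and the zero or negative interactions in expected counts follow from the structure, for the count patterns shown. The rejection percentages do not: rates, variances and month-6 use are assumed, and for a doubling with continued use the interaction result runs from 0% to 54% by SE type and model. They are illustrations, not this trial's power. The link from the listed measures to penetration is inferred.

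**What to change.** For dashboard use and treatment initiation:
- Name the month-3 IF/EF contrast as the test of the strategy effect, from a model with categorical time or from month 3 alone, with a site random effect and a small-cluster t reference.
- Leave out the uninformative month-0 row.
- Use the same month-3 outcome in the Aim 2 penetration mediation model in place of the growth parameter.
- Report month 6 separately, and only for measures that can still occur after the app uninstalls.
- Define penetration, and state the time coding, the SE type and the model for each component.

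This is SAP wording and needs no new penetration data.

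A separate point, which adds no weight to the one above: protocol sections 4.1 and 8.2 survey staff at 0 and about 3 months, while the SAP analyses acceptability at 6 months as well. Reconcile them. If no 6-month survey is scheduled, restate acceptability as a 0/3-month outcome. If a 6-month value is wanted, the items could join the 6-month absorptive-capacity assessment listed in section 5.1; a separate paid survey would cost $20 × 100 = $2,000.
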